### Exclusion Criteria

The underarm body temperature on the day of enrollment was  $> 37.0^{\circ}\text{C}$ .

Have been suffering from influenza within the previous 3 months (confirmed by either clinical, serological or microbiological methods).

Any previous influenza vaccination (registered or experimental) within 6 months or any planned influenza vaccination during the study period.

Allergic to any component of the vaccine, a history of allergic reactions to eggs or gentamicin sulfate.

A history of severe allergy to any vaccine or drug.

Preterm birth (delivered before 37 weeks of gestation), low birth weight baby (birth weight  $< 2300\text{g}$  for girls,  $< 2500\text{g}$  for boys).

Dystocia, asphyxia rescue, nervous system damage history;

Congenital malformations or developmental disorders, genetic defects, severe malnutrition, etc.

Acute illness, severe chronic illness or acute attack of chronic disease on the day of vaccination;

A history of live attenuated vaccination within 14 days prior to vaccination and a history of other vaccinations within 7 days prior to vaccination;

Patients who received immunoenhancement or inhibitor therapy within 3 months (continued oral or intravenous administration for more than 14 days);

Congenital or acquired immune deficiency, HIV infection, lymphoma, leukemia or other autoimmune diseases;

History of asthma, past two years of instability requiring emergency treatment, hospitalization, intubation, oral or intravenous administration of corticosteroids;

Have received blood or blood-related products;

A history of convulsion, epilepsy, encephalopathy, guillain-barre syndrome, a history of mental illness or a family history;

A history of abnormal coagulation function (such as coagulation factor deficiency,

coagulation disease);

Planning to relocate before the end of the study or to leave for an extended period during the scheduled study visit;

Participating in or planning to participate in other clinical trials in the near future;

The investigators determined that any conditions were inappropriate to participate in the clinical trial.

## DATA STATISTICS

### Statistics analysis of immunogenicity

The prevaccination and postvaccination geometric mean of antibody and its 95% confidence interval (confidence interval, CI) will be described. The postvaccination serum conversion rate and protection rate of antibody and their 95% CI will be described.

Comparisons will be conducted to evaluate differences in response between study groups using a  $\chi^2$  test or Fisher's exact test to compare to the difference of serum conversion rate and protection rate. Statistical significance will be considered at a level of  $\alpha = 0.05$  and all tests will be 2-sided.

If serum HI antibody conversion rate is more than 40%; protection rate more than 70%; GMI more than 2.5 folds, the immunogenicity will reach the design requirements.

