At the same time, several studies showed that the influenza vaccine induces a poor immune response in young children. Unvaccinated children below 3 years old were induced by vaccine weaker than unvaccinated children above 3 years old younger or vaccinated children below 3 years old, especially for the B subtype influenza virus. For 6 ~ 35 months old children were recommended vaccination dosage of 0.25 ml antigen of influenza inactivated vaccines. This recommendation was based on the observation in the 1970s of increased adverse reactivity in younger children with an adult's dosage of whole-virus inactivated influenza vaccines, especially the fever. but at present in the seasonal flu vaccine has been without the use of an inactivated virus. The safety and immunogenicity of 0.5ml and 0.25ml dosage antigen of vaccine were evaluated in 6~35 months children in a large number of clinical trials. The results showed that the high dosage of the split vaccine was well tolerated and could induce a strong immune response. Hence, in 2016, the FDA approved the adult dosage of the influenza vaccine for children above 6 months. Besides, many countries such as Canada, Brazil, Mexico, Finland, and Britain approved dosage of 15µg and

7.5 µg antigen for children below 3 years.

Given the situation of children-using the influenza vaccine, we carried out the clinical trial of the quadrivalent influenza vaccine suitable for children aged 6 to 35 months, which is of great significance for children to prevent influenza in China.

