## STUDY DESIGN

A randomized, double-blind, parallel control design was set to enroll 1,980 healthy subjects aged 6-35 months. Subjects were randomly inoculated with experimental vaccine 1, experimental vaccine 2, control vaccine 1 or control vaccine 2 in a ratio of 2:2:1:1 for safety and immunogenicity evaluation. The inoculation time was 0 and 28 days.

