## STUDY ENDPOINT

### Immunogenicity

(1) 28 days after receiving two doses of vaccine in subjects aged 6-35 months, seroconversion rate of HI antibodies against any subtype of influenza virus in each group.

(2) 28 days after receiving two doses of vaccine in subjects aged 6-35 months, seroprotection rate of HI antibodies against any subtype of influenza virus in each group.

(3) 28 days after receiving two doses of vaccine in subjects aged 6-35 months, GMT and GMI of HI antibodies against any subtype of influenza virus in each group.

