## **EVALUATION CRITERIA OF SAFETY**

The safety evaluation of each group will be divided into three stages. From the first dose inoculation to day 7 after inoculation; From the first dose inoculation to day 21 after inoculation; From the second dose inoculation to day 30 after the second dose inoculation. The first stage is the basis for the follow-up group of the same vaccine, and will be carried out under blind. The latter two stages are the basis for evaluation of vaccine safety, and will be carried out under unblind. If each evaluation is not found level 4 local and systemic adverse reactions associated with vaccine and the total incidence rate of level 3 of local and systemic adverse reactions and abnormal laboratory test which associated with the vaccination is lower than 15%, that the vaccine will be acceptable safety.

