## **ELIGIBILITY**

Inclusion Criteria

Healthy infants aged 6-35 months.

Volunteer legal guardian or client informed consent, voluntarily participate in and sign informed consent.

The volunteer legal guardian or client has the ability (non-illiterate) to understand the study procedures, to use a thermometer, scale, and fill in a diary card as required, and be able to complete the clinical study in compliance with the clinical trial protocol.

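### The pooled immunogenicity and Grade 3 criteria and the unadjusted group comparisons cannot show an age difference within 6-35 months; an age-stratified comparison and a descriptive age-band table would, at almost no cost

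*Combined protocol and SAP*

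**What the plan says.** All references are to the combined protocol and SAP.

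- **Population.** ELIGIBILITY admits "Healthy infants aged 6-35 months". STUDY DESIGN plans to "enroll 1,980 healthy subjects aged 6-35 months", allocated "in a ratio of 2:2:1:1 for safety and immunogenicity evaluation". It names no stratification factor and describes no randomisation procedure. The design table under Safety observation has a single age row.
- **Endpoints.** Each immunogenicity endpoint covers the whole range, for example "28 days after receiving two doses of vaccine in subjects aged 6-35 months, seroprotection rate of HI antibodies".
- **Acceptance rules.** EVALUATION CRITERIA OF IMMUNOGENICITY, repeated under DATA STATISTICS, requires seroconversion above 40%, seroprotection above 70% and GMI above 2.5. EVALUATION CRITERIA OF SAFETY requires no vaccine-related Grade 4 reaction, and passes the related Grade 3 rate if it "is lower than 15%, that the vaccine will be acceptable safety". Neither section splits by age.
- **Comparisons.** "Comparisons will be conducted to evaluate differences in response between study groups" with chi-square or Fisher's exact test, two-sided at 0.05. The safety section uses the same tests for adverse event rates. No age adjustment or age summary appears.
- **Background on age.** It says "several studies showed that the influenza vaccine induces a poor immune response in young children". It traces the 0.25 ml recommendation for this age range to a 1970s observation of "increased adverse reactivity in younger children with an adult's dosage of whole-virus inactivated influenza vaccines, especially the fever".

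**The concern.** A pooled rate is an average weighted by whatever age mix is recruited, and the plan neither fixes nor reports that mix. If response or reactogenicity differs between infants and older toddlers, a group can meet the pooled limits while its youngest members miss them, and no planned table would show it. The verdict would still be worded for 6-35 months and, by the stated objective, would be carried into phase III planning.

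A lesser point is that the crude comparisons leave any chance age imbalance between arms in the estimated difference, when adjusting for a baseline value already collected would remove it.

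**Working it through.** **1. The plan's own figure.** The only size figure is 1,980. The design table gives 660 + 330 + 330 + 660 = 1,980. The 2:2:1:1 ratio, in the order experimental 1, experimental 2, control 1, control 2, gives 660 + 660 + 330 + 330 = 1,980. The totals agree, but the sizes of experimental vaccine 2 and control vaccine 2 do not. Both arm sizes, 330 and 660, are carried below. No power, expected rate, dropout or age mix is stated, so there is nothing further to reproduce.

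**2. Inputs that are assumptions.** The bands are 6-11, 12-23 and 24-35 months. Uniform enrolment over 30 months of age gives shares of 6/30 = 20%, 12/30 = 40% and 40%. The band rates are illustrative.

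**3. Illustration.** Pooled rate = sum of share × band rate.
- Seroprotection 50%, 70%, 82%: 0.2×0.50 + 0.4×0.70 + 0.4×0.82 = 0.708, which passes.
- Related Grade 3 35%, 10%, 9%: 0.2×0.35 + 0.4×0.10 + 0.4×0.09 = 0.146, which passes.

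**4. How far the youngest can fall short.** With youngest share w, limit T and older-child rate p, the break-even rate in the youngest is (T − (1−w)p)/w. For GMI the formula is applied to logarithms. Examples with w = 0.20 are (0.70 − 0.8×0.80)/0.2 = 0.30 and (0.15 − 0.8×0.05)/0.2 = 0.55. Uniform enrolment gives w = 0.20 for 6-11 months and 0.60 for 6-23 months; 0.40 is an intermediate value.

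| w | Seroprotection (older 80%) | Seroconversion (older 60%) | GMI (older 4) | Related Grade 3 (older 5%) |
|---|---|---|---|---|
| 0.20 | 30% | passes even at 0% | passes even with no rise | 55% |
| 0.40 | 55% | 10% | 1.24 | 30% |
| 0.60 | 63% | 27% | 1.83 | 22% |

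The result depends on p. With w = 0.20 and older children at 75% rather than 80%, the seroprotection break-even is (0.70 − 0.8×0.75)/0.2 = 50%.

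**5. Chance of a pooled pass.** Take w = 0.20, youngest 50% and older 80%. The true pooled rate is 0.2×0.50 + 0.8×0.80 = 74%. In simulation the observed pooled rate exceeds 70% with probability about 99% (660 children) or 95% (330 children).

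**6. What a band table can show.** A 20% band holds 132 of 660 or 66 of 330 children. The 95% half-width at 70% is 1.96×√(0.7×0.3/132) = 7.8 points or 1.96×√(0.7×0.3/66) = 11.1 points. If the true youngest rate is 50%, the upper exact 95% limit falls below 70% with probability about 99.5% (132 children) or 92% (66 children). Arm comparisons inside that band would be weak. For an assumed 60% against 70%, power falls from 97% to 40% (660 v 660), from 88% to 29% (330 v 660) and from 77% to 22% (330 v 330).

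**7. What adjustment gains.** With the step 3 seroprotection rates, the between-band variance is 0.2×(0.50−0.708)² + 0.4×(0.70−0.708)² + 0.4×(0.82−0.708)² = 0.0137. The total variance is 0.708×0.292 = 0.207, so age accounts for about 7%. For 330 v 660, chance age imbalance moves the difference by about 1.96×√(0.0137×(1/330 + 1/660)) = 1.5 points. Total sampling error is about 1.96×√(0.207×(1/330 + 1/660)) = 6.0 points.

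**The case against.** The strongest reply is that the documents do not say response varies with age inside the enrolled range. The response contrast in BACKGROUND INFORMATION sets unvaccinated children under 3 years against unvaccinated children over 3 or vaccinated children under 3, and every participant is under 3. The fever remark concerns 1970s whole-virus vaccine; the same section says that type is no longer in use and that the higher dosage of split vaccine was well tolerated, with a strong response, at 6-35 months. A reader might infer that the plan contradicts its own evidence on age. It does not, and this reply stands. There is at most an indirect link: the prior-vaccination contrast does lie inside the enrolled range, and prior vaccination plausibly rises with age, but the documents do not state that.

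A reader might also infer that the crude tests are biased or that the whole safety verdict can be diluted. Neither holds. Under randomisation the unstratified tests are valid and chance age imbalance is already part of their sampling error. One related Grade 4 reaction at any age fails the safety rule.

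Two further points carry some weight. The trial supports phase III planning and is not presented as an age-specific licensing claim. Also, the absence of age strata is read from silence, since no randomisation procedure is described. Neither point explains why the reported verdict should carry no view of age at all.

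**Conclusion.** The point holds in a limited form. As written, the three immunogenicity criteria and the 15% related Grade 3 criterion are judged on pooled groups, and the comparisons ignore age. Under the assumed mixes, the youngest infants could be 20 or more points below the seroprotection limit while the pooled criterion is met. With smaller age differences, or older children only just above the limit, the masking shrinks. This shows what the plan could not detect; it is not evidence that such a gradient exists.

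For the comparisons, adjustment brings a modest gain in precision (about 7% of outcome variance under the illustrative rates) and corrects no bias. The change is worth making because it is nearly free and better supports a statement about the full 6-35 month range.

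**What to change.** First reconcile the allocation ratio in STUDY DESIGN with the arm sizes in the design table, because the band sizes depend on them. Then amend both the immunogenicity and the safety parts of DATA STATISTICS, before unblinding:

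- Prespecify age bands, for example 6-11, 12-23 and 24-35 months. The documents give no cut-points, so the sponsor should justify its choice.
- For between-group rates, replace the crude chi-square test by a Cochran-Mantel-Haenszel test with a band-stratified difference and 95% CI. Use an exact stratified version where Fisher's test would have applied.
- Beside the pooled verdict, report seroconversion, seroprotection, GMI and the related Grade 3 rate with 95% CIs by band and arm. Label these descriptive, and do no between-arm tests within bands.

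The pooled verdict should not be made to depend on any one band's interval. In a quadrivalent arm that would add 3 bands × (4 strains × 3 criteria + 1 Grade 3 rate) = 39 checks with no multiplicity control.

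The cost is a few lines of text and one set of tables, with no new data or children. The downside is imprecision: about 11 points half-width at 70% for a 20% band in a 330-child arm. If unblinding has already taken place, the same analyses should be reported as post hoc.

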## STUDY OBJECT

To evaluate the immunogenicity and safety of 2 doses of quadrivalent influenza virus split vaccine (0.25ml/ dose and 0.5ml/ dose) in healthy population aged 6-35 month., so as to provide a data support for phase III clinical trials.

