### Statistics analysis of safety

After the first dose inoculation and the second dose inoculation, the number of adverse reactions (rate), number of cases and adverse reaction grade were recorded.

The number of adverse events after inoculation will be described.

Comparisons will be conducted to evaluate differences in response between study groups using a  $\chi^2$  test or Fisher's exact test to compare to the difference of adverse events rate. Statistical significance will be considered at a level of  $\alpha = 0.05$  and all tests will be 2-sided.

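### Response and adverse event rates in four arms are compared only by χ² or Fisher p-values, with no named contrast and no confidence interval for any between-group difference

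*Combined protocol and SAP*

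**What the plan says.** The Study Design section describes a trial that "was set to enroll 1,980 healthy subjects aged 6-35 months", randomised to two experimental and two control vaccines. The Study Object section gives the aim as evaluating the 0.25 ml and 0.5 ml doses, "so as to provide a data support for phase III clinical trials".

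Under Data Statistics, the immunogenicity section plans estimation first: "The postvaccination serum conversion rate and protection rate of antibody and their 95% CI will be described". The Study Endpoint section defines these rates for each group, so the intervals are naturally read as per-group intervals. The between-group plan then follows: "Comparisons will be conducted to evaluate differences in response between study groups". The methods named for both rates are the χ² and Fisher exact tests. The significance level is 0.05 and "all tests will be 2-sided".

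The safety section repeats the same tests "to compare to the difference of adverse events rate", and plans no confidence interval for adverse event rates, per group or between groups.

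Neither section names a pair of arms, a reference arm, an order of testing or a multiplicity rule. Neither says whether the test is one four-group test or a set of two-group tests.

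**The concern.** A phase II trial that feeds a phase III design has to show how large the difference is between the two volumes and between each experimental vaccine and a comparator, and how uncertain each difference is. The only comparative output planned here is a p-value over unspecified groups. The acceptance criteria (seroconversion above 40%, seroprotection above 70%, GMI above 2.5) are absolute thresholds and compare nothing with anything, so they do not fill the gap.

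Two things are at stake. First, which comparisons are made is left open until the data are unblinded. Second, a p-value above 0.05 says nothing about how large a difference the data still allow, and a reader planning phase III could take it as showing no difference.

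**Working it through.** The documents give no power statement, target difference or expected rate, so there is no design figure to reproduce. The calculations below rest on assumed rates.

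**Inputs.** Total 1,980 (Study Design). The ratio 2:2:1:1 in that section gives 1980 × 2/6 = 660 for each experimental vaccine and 1980 × 1/6 = 330 for each control. The table under Safety Observation, as extracted, lists 660, 330, 330 and 660 for experimental 1, experimental 2, control 1 and control 2. Both sets sum to 1,980 but put the sizes on different arms, so both are carried forward. All enrolled children are taken as evaluable. The base response is assumed to be 70% (the seroprotection threshold), with 50% and 80% as a range.

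**Sizes of the natural contrasts.** These are experimental 1 v experimental 2, and each experimental vaccine v the control of the same number. (The pairing by number is an assumption.)
- By the ratio in the text: 660 v 660, 660 v 330, 660 v 330.
- By the table: 660 v 330 for all three.

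**Half-width of the 95% interval for a difference**, 1.96 × √[p(1−p)(1/n₁ + 1/n₂)]:
- 660 v 660, p = 0.70: 1.96 × √(0.21 × 0.003030) = 1.96 × 0.02523 = 0.049.
- 660 v 330, p = 0.70: 1.96 × √(0.21 × 0.004545) = 1.96 × 0.03090 = 0.061.
- At p = 0.50: 0.054 and 0.066. At p = 0.80: 0.043 and 0.053.

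**What a near miss leaves open.** If the observed difference is just short of significance, it is about one half-width from zero, and the upper limit is about two half-widths: 2 × 4.9 = 9.8 points and 2 × 6.1 = 12.2 points, so about 10 to 12. Over base rates of 50% to 80% the range is 2 × 4.3 = 8.6 to 2 × 6.6 = 13.2 points.

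**Worked example (assumed rates).** Take 70% of 660 against 64% of 330.
- Pooled rate: (0.70 × 660 + 0.64 × 330)/990 = 0.68.
- Test: standard error √(0.68 × 0.32 × 0.004545) = 0.03145; z = 0.06/0.03145 = 1.91; p = 0.056.
- Interval: unpooled standard error √(0.21/660 + 0.2304/330) = 0.03188; 0.06 ± 1.96 × 0.03188 gives −0.2 to +12.2 points.

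The planned output is a non-significant p-value. The interval shows that a 12-point difference is not excluded.

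**The two readings of the test.**
- One four-group test has 3 degrees of freedom. Rejection says that not all four rates are equal, and does not say which differ.
- Two-group tests on four arms give 4 × 3/2 = 6 pairs per strain and rate. With four strains and two rates that is 6 × 4 × 2 = 48 possible tests. For one strain and rate, six independent tests at 0.05 would have a family-wise error of 1 − 0.95⁶ = 0.26. This is an approximation only, because the pairs share arms.

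**The case against.** The plan does give material for an effect size. Immunogenicity rates with 95% intervals are planned and the endpoints are defined by group, so a reader can subtract two rates and approximate an interval from the arm sizes. This stands: it would be wrong to say the plan yields no effect size. What is missing is a prespecified difference with its interval for named pairs. For adverse events even the per-group interval is absent.

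The plan also claims neither equivalence nor non-inferiority, and its immunogenicity decision rule does not use the between-group p-value. This stands too, and limits the harm. The misreading of p > 0.05 is a risk, not something the plan commits.

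A reader might go further and infer that the plan specifies a single four-group test and so loses power. The documents do not support this. They speak of comparisons in the plural and of two-sided tests, which fits two-group tests at least as well. Nor is the loss general. With 660/660/330/330 and assumed experimental rates of 63% and 70%, the direct contrast has 77% power. The four-group test has 61% if both controls lie midway at 66.5%, but 74% if both are at 63%, 75% if both are at 70%, and 80% if there is one at each.

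A reader might also take a wider range than 10 to 12 points at 70% response by using two arms of 330. None of the contrasts above, paired by number, has those sizes under either set of arm sizes.

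**Conclusion.** The concern holds in this form: across four arms the only between-group method for the response and adverse event rates is a p-value, with no contrast named and no interval for a difference, in a trial meant to inform phase III. A four-group rejection would not locate the difference, and pairwise testing would leave up to six unadjusted comparisons per strain and rate. At an assumed 70% response with everyone evaluable, a result just short of significance leaves a true difference of about 10 to 12 points possible. Losses to follow-up would widen this.

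The conclusion about missing contrasts and intervals rests on the text alone. The size rests on the assumed rate and on arm sizes that the documents state in two ways, unless the table was damaged in extraction. The documents also do not say which volume belongs to which experimental vaccine or what each control is, so treating experimental 1 v experimental 2 as the volume contrast is an assumption. The trial data remain usable. This is a change that should be made to the analysis plan, not a flaw that undermines the trial.

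**What to change.** 1. State which volume and which control belong to which arm, and reconcile the arm sizes in the Study Design text with those in the table under Safety Observation.
2. In the immunogenicity and safety analysis sections, replace the general group comparison with contrasts named in advance: experimental 1 v experimental 2, and each experimental vaccine v a control that the sponsor specifies.
3. For each contrast, report the difference in seroconversion and seroprotection by strain, and in adverse event rates, with a two-sided 95% interval (Miettinen-Nurminen or Newcombe).
4. Keep the χ² or Fisher p-values as supportive, and say whether they are adjusted for multiplicity.
5. State that p > 0.05 is not read as equivalence.

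The cost is SAP wording and a few extra table columns. No new participants, data or margin are needed.
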